Individuals with episodic migraine will be considered for participation in this study. Primary inclusion criteria will be (1) age 18-64 years old, (2) history of migraine with or without aura, based on the International Classification of Headache Disorders (3rd edition) for at least 3 years, (3) two or more migraine attacks per month on average during the previous year, and (4) ability to communicate in English (in order to understand and follow instructions of testing). Exclusion criteria will include: (1) fifteen or more headache days per month; (2) aspirin or NSAID-induced asthma or allergy; (3) pregnancy and/or lactating; (4) history of coronary artery bypass surgery, heart attack, angina, stroke, serious gastrointestinal bleeding, peptic ulcer disease; or chronic kidney disease; (5) having medical conditions requiring use of diuretics or daily anticoagulants; (6) having severe uncontrolled medical problems or medications that may influence measurements or impair ability to participate in the testing (e.g. daily or frequent use of opiates or barbiturates (>8 days per month), or NSAIDs or other analgesics (>14 days per month); known creatinine > 2.5 mg/dl or GFR < 30, severe peripheral neuropathy, dementia, etc.); and (7) having been advised by a health professional not to use COX-2 inhibitors.

Potential participants will be recruited from the Hartford Healthcare Headache Program.

Randomized controlled trial: After screening, which will be performed on a non-migraine day, participants will be randomized in a double-blinded fashion to receive either the active drug (DFN-15) or placebo in a ratio of 4:1. They will be instructed to return to the

clinic during a migraine. At the ‘during-migraine’ visit, which will begin 3 hours after onset of headache, we will document headache intensity, associated symptoms, and mechanical and heat pain threshold (first) before treatment (at 180 min after onset of headache) and (second) at a 120 min after treatment (5 hours after headache onset). Based on our prior experience studying migraine patients, we plan to screen 100 patients to achieve 50 participants completing the 2 study visits as planned. 80/100 patients will be randomized to receive the active drug and 20/100 patients will receive the placebo. The study will be terminated as soon as the first 40 patients who received the DFN-15 and first 10 patients who received placebo completed visit 2.

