Screening visit - In the first appointment we will identify patients who are good candidate to participate in the study and measure their pain thresholds following an initial evaluation. This appointment will allow us to train patients in how the quantitative sensory testing is performed.

‘During-migraine’ visit – In the second appointment patients’ headache intensity, associated symptoms, and mechanical and heat pain thresholds will be tested 180 min after the onset of a migraine headache. Pain threshold will be determined within the referred pain area in the head. These tests will provide the pre-treatment data to be compared later with post-treatment data. Once pain thresholds are established, patients will be treated and their headache intensity, associated symptoms and pain thresholds will be re-examined 120 minutes later.

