Throughout the treatment and testing the patients will be monitored (vitals, etc.) to ensure their safety. If a member of the control group is in excruciating pain and their migraine is intolerable they will be prescribed a rescue medication. In this case the participant will drop out of the study. The participants will have the option to drop out at any point in the study. At the end of the testing (5 hours after migraine onset), if a participant (from either group) is still symptomatic and in pain, they will have the opportunity to have a rescue medication prescribed by one of the specialists at the Headache Center. In the case that a patient does not respond well to the study treatment they will be monitored for at least 1 hour before leaving the clinic.

Data analysis:

Primary endpoint: There are 2 primary endpoints in this study. The first is reduction in headache intensity after DFN-15 treatment, and the second is reduction in skin sensitivity at 2 hours after DFN-15 treatment.

For reduction in headache intensity, level of pain will be documented at 1 and 2 hours after treatment using a visual analogue scale of 0 (no pain) to 10 (worst pain). Comparisons of these ordinal (repeated) measures will be performed using Friedman two-way analysis of variance followed by Wilcoxon matched-pairs signed-ranks test.

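### Early rescue is written for the control group only, which blinded staff cannot apply, and the plan does not say how a patient rescued before 2 hours counts in the >50% headache responder outcome

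*Combined protocol and SAP*

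**What the plan says.** **Rescue (Patient Safety).** There are two rules. The first covers the time before testing ends: "If a member of the control group is in excruciating pain and their migraine is intolerable they will be prescribed a rescue medication". Its consequence is "In this case the participant will drop out of the study". The second applies at the end of testing, 5 hours after onset: "if a participant (from either group) is still symptomatic and in pain, they will have the opportunity to have a rescue medication prescribed". The same section adds "The participants will have the option to drop out at any point in the study", but it describes no early rescue for a DFN-15 patient.

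**Blinding and accrual (Randomized controlled trial paragraph).** "participants will be randomized in a double-blinded fashion to receive either the active drug (DFN-15) or placebo in a ratio of 4:1". No unblinding step is described. The study is to be "terminated as soon as the first 40 patients who received the DFN-15 and first 10 patients who received placebo completed visit 2".

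**Outcome (Data analysis).** The primary outcome measure is the share of patients whose headache intensity falls by more than 50% from before to after treatment. It is compared between arms by a Z test and a chi-square test. The defining sentence gives no time point, but the study design sets the post-treatment assessment at 2 hours. In the 'During-migraine' visit paragraph, for example, "their headache intensity, associated symptoms and pain thresholds will be re-examined 120 minutes later". Data analysis also says "level of pain will be documented at 1 and 2 hours after treatment".

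**Analysis set.** The only sentence restricting analysis to completers of all three sessions is in the skin-sensitivity paragraph. It follows a sentence limited to that endpoint and to pain-threshold measurements. No sentence assigns an outcome to a patient rescued before 2 hours.

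**The concern.** There are two linked problems.

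1. A rule that depends on being a control cannot be followed by people who do not know who the controls are. Staff must either look up allocation, which unblinds them before a subjective 2-hour score, or depart from the text by treating both arms alike or rescuing no one. Read literally, the rule also leaves a DFN-15 patient in intolerable pain with only the option to withdraw.

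2. A patient rescued before 2 hours is very likely a treatment failure. Leaving such patients out of the responder proportion raises the observed response in whichever arm they leave. The stopping rule counts visit 2 completers, so a later completer would take the rescued patient's place. At stake are the accuracy of the two reported response rates and, if only placebo patients are rescued, part of the trial's power.

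**Working it through.** **Inputs from the plan (end of Data analysis).** Response 80% on DFN-15 and 30% on placebo; one-tailed 5% level, critical Z 1.645 in absolute value; power 90%; allocation 4:1; 36 and 9 required. The stopping rule gives 40 and 10 completers.

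**Assumed input.** r is the share of non-responders rescued after dosing and before the 2-hour score. The documents give no value. I use r = 10%, 20% and 30% as illustrations, not bounds, and take every rescued patient to be a true non-responder.

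**Step 1: reproduce the plan's sample size.** With k = 4, the pooled rate is (0.30 + 4 × 0.80)/5 = 0.70.

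n(placebo) = [1.645 √(0.70 × 0.30 × 1.25) + 1.282 √(0.30 × 0.70 + 0.80 × 0.20/4)]² / 0.50² = 8.80, rounded up to 9, with 36 on DFN-15.

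This matches the plan. Exact power, by binomial enumeration of the pooled one-tailed Z test, is 0.903 at 36/9 and 0.927 at 40/10.

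**Step 2: observed response if rescued patients are excluded.** Observed rate = p / [p + (1 − p)(1 − r)].

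- Placebo, p = 0.30: 0.30/0.93 = 32%; 0.30/0.86 = 35%; 0.30/0.79 = 38%.
- DFN-15, p = 0.80, r = 30%: 0.80/0.94 = 85%.

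A count check: with 3 responders among 10 placebo patients, excluding 2 of the 7 non-responders (29%) turns 3/10 = 30% into 3/8 = 37.5%.

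**Step 3: rescue on placebo only, rescued patients excluded.**

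| r | Placebo observed | Difference from 80% (points) | Power 36/9 | Power 40/10 | One-sided error 40/10* |
|---|---|---|---|---|---|
| 0 | 30% | 50 | 0.903 | 0.927 | 0.050 |
| 10% | 32% | 48 | 0.877 | 0.905 | 0.038 |
| 20% | 35% | 45 | 0.844 | 0.875 | 0.027 |
| 30% | 38% | 42 | 0.799 | 0.833 | 0.018 |

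*True response 30% in both arms.

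**Step 4: rescue applied blind to both arms, rescued patients excluded.** At r = 30% the observed rates are 85% and 38%, a difference of 47 points. Power is 0.894 at 36/9 and 0.914 at 40/10, about 1 point below the no-rescue figures. One-sided error at 40/10 stays at 0.050 to 0.051 for every r used.

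**Step 5: rescue in both arms, rescued patients kept and counted as non-responders.** The target rates return to 80% and 30%. Accruing to 40/10 completers and analysing the rescued patients with them gives power 0.934, 0.941 and 0.949 for r = 10%, 20% and 30%. One-sided error is 0.046, 0.045 and 0.045. Expected numbers dosed at r = 30% are 40/(1 − 0.20 × 0.30) = 42.6 on DFN-15 and 10/(1 − 0.70 × 0.30) = 12.7 on placebo.

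**The case against.** **The control-group wording may be loose drafting.** Staff who keep the blind would rescue either arm or neither, and nothing shows that they would check allocation. This is fair: the unblinding harm is conditional and cannot be sized. The printed sentence is still unworkable under blinding, and the contrast with the 5-hour rule, which names both groups, makes it hard to read as neutral.

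**Exclusion may be the plan.** Rescued patients leave the study, accrual runs to completers, and the sample size carries a 20% dropout allowance. These do point towards a completers analysis. But the completers-only sentence is written for skin sensitivity, so the question stays open for headache. If exclusion is intended, the analysis drops patients because treatment failed.

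**The effect is small and assumed.** Of 10 placebo patients, 7 are expected non-responders, so r = 10% to 30% is 0.7 to 2.1 people over a 2-hour window. At 40/10 and r = 10%, power is still above 90%. This stands, and it limits the weight of the point.

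**Stronger readings that the documents do not support.**

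- A reader might infer that excluding rescued patients favours DFN-15. The rule as written removes placebo failures, so it works against DFN-15 and lowers one-sided error. Error above 5% from excluding failures would need DFN-15 failures alone to leave, and the text offers no mechanism for that.
- A reader might infer that the responder outcome has no time point. Its defining sentence lacks one, but the study design sets the assessment at 2 hours.

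**Conclusion.** The point holds. The early-rescue sentence conflicts with the double-blind design as written, and the handling of early-rescued patients in the >50% responder outcome is unstated, with the surrounding text leaning towards exclusion. It should be fixed, although the numerical effect is modest.

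If only placebo patients are rescued and they are excluded, power at 40/10 falls from 0.93 to 0.91, 0.88 or 0.83 at the three assumed rates, and false positives become less likely. If rescue is applied blind to both arms, the power loss is about 1 point and the main harm is that both response rates are overstated. All of this rests on the assumed rescue rates, on rescued patients being true non-responders, and on the plan's 80% and 30%. The sample size calculation itself is not in question.

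**What to change.** **Patient Safety.** Replace the control-group sentence with an arm-neutral one, for example: *Any participant in either group whose pain becomes intolerable after dosing may receive rescue medication; the time is recorded, and allocation is not consulted.* No clinical threshold is proposed here.

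**Data analysis.** Add for the >50% responder outcome: *The outcome is assessed 2 hours after dosing. Patients who receive rescue after dosing and before the 2-hour score are included and counted as non-responders in both groups.*

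**Reporting.** Tabulate rescues and other withdrawals by arm with reasons, and add a completers-only sensitivity analysis.

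**Leave unchanged.** Keep the 40/10 completer target and the completers-only set for the skin-sensitivity tests.

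**Do not extend the rule to other withdrawals.** Counting withdrawals unrelated to rescue as non-response in the main analysis carries its own cost. If 10% of placebo patients alone left for reasons unrelated to response, one-sided error would be about 0.07. If 10% of both arms did so, power with 40/10 completers would be about 0.88.

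**Cost.** Mainly wording. Arm-neutral rescue may mean dosing a few more DFN-15 patients, about 42.6 rather than 40 at r = 30%. The reported DFN-15 response may read lower than among completers, 80% rather than 85% in that case.

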between before and after DFN-15 treatment will be computed on a pair-wise basis. To increase the sensitivity of detecting changes, patients in this study will be compared to themselves (baseline vs. during untreated migraine vs. during treated migraine) rather than to control subjects because the large normative range of pain thresholds reduces the sensitivity of detecting allodynia in reference to the normal range. Differences between pain-free vs. during untreated migraine vs. during treated migraine will be computed on a multiple sample pair-wise basis. Differences in mean pain threshold will be judged (significant or not significant) by using appropriate pair-wise multiple sample comparison (Newman-Keuls, Kruskal-Wallis) tests. Alternatively, repeated measurements of pain thresholds (allodynia) will be analyzed using Friedman two-way analysis of variance. Finally, secondary analyses using the collected data may be done as a part of this study including, but not limited to, the duration and intensity of the headache prior to arrival at the clinic.

The primary outcome measure in the current study is the proportion of patients demonstrating a headache intensity decrease that is greater than 50% (post-treatment compared to pre-treatment). Secondary outcome measures are proportions of patients demonstrating allodynia before and after treatment; allodynia to thermal stimuli is defined as a pain threshold < 41 0C, and to mechanical stimuli as pressure pain threshold of < 30 g.

The primary and secondary outcome measures will be examined using the Z test for comparison of independent proportions and Chi-square (χ^2) test to assess the categorical association between the group (treatment / placebo) and (i) reduction rate of headache intensity (below / above 50%; primary outcome measure); (ii) proportion of thermally allodynic participants (pain threshold below / above 41 0C; secondary outcome measure); and (iii) proportion of mechanically allodynic participants (pressure pain threshold below / above 30 g; secondary outcome measure).

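### The plan names two within-patient primary endpoints in one place and a single between-arm responder primary in another, and leaves the sidedness and direction of the deciding test open

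*Combined protocol and SAP*

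**What the plan says.** All of this stands in the current text of the combined protocol and SAP, mostly under Data analysis.

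- **Primary endpoint paragraph.** It opens with "There are 2 primary endpoints in this study" and takes these to be headache intensity and skin sensitivity, each as a reduction following DFN-15, with no comparison arm named. Pain is scored from 0 to 10 at 1 and 2 hours. "Comparisons of these ordinal (repeated) measures will be performed using Friedman two-way analysis of variance followed by Wilcoxon matched-pairs signed-ranks test".
- **Skin-sensitivity paragraph.** Thresholds are compared across pain-free, untreated-migraine and treated-migraine conditions: "patients in this study will be compared to themselves (baseline vs. during untreated migraine vs. during treated migraine) rather than to control subjects". "Differences in mean pain threshold will be judged (significant or not significant) by using appropriate pair-wise multiple sample comparison (Newman-Keuls, Kruskal-Wallis) tests". Friedman is offered as an alternative.
- **Outcome-measures paragraphs.** "The primary outcome measure in the current study is the proportion of patients demonstrating a headache intensity decrease that is greater than 50" per cent. "Secondary outcome measures are proportions of patients demonstrating allodynia before and after treatment". "The primary and secondary outcome measures will be examined using the Z test for comparison of independent proportions and Chi-square", here relating treatment group to headache response, thermal allodynia and mechanical allodynia. No sidedness is given.
- **Power paragraph.** A Z test for independent proportions with alpha 5%, power 90%, 4:1 allocation, one tail and critical Z of -1.645. The one tail is justified by expecting a lower outcome under treatment. The assumed responder proportions are 80% (treatment) and 30% (placebo), giving 36 + 9 patients.
- **Randomized controlled trial paragraph.** Double-blind, and stopped once 40 DFN-15 and 10 placebo patients have completed visit 2.

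**The concern.** Skin sensitivity is primary in one paragraph and secondary in another. Headache intensity is a within-patient change in one and a between-arm responder proportion in the other. No sentence ranks the two statements, and no multiplicity rule covers two primaries.

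The two versions answer different questions. A change from before to after dosing mixes drug effect with placebo response and the natural course of the attack. The plan's own figures show that this matters: 30% of placebo patients are expected to improve by more than 50%. While the first statement stands, a before-after result could be declared a met primary endpoint of a placebo-controlled trial without any comparison with placebo.

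Even if the responder comparison governs, its test is not fully fixed. Sidedness is stated only for the power calculation, the stated direction conflicts with the assumed proportions, and the time point is given only as post-treatment although pain is scored at 1 and 2 hours. Any of these left open could be settled after the data are seen.

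**Working it through.** **1. The two statements side by side**

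| | Primary endpoint and skin-sensitivity paragraphs | Outcome-measures and power paragraphs |
|---|---|---|
| Number of primaries | 2 | 1 |
| Headache | reduction after DFN-15 | proportion with >50% decrease |
| Skin sensitivity | primary | secondary (allodynia proportions) |
| Contrast | within patient, across times or conditions | DFN-15 vs placebo |
| Tests | Friedman, Wilcoxon matched pairs, Newman-Keuls, Kruskal-Wallis | Z, chi-square |
| Powered | no | yes (responders only) |

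As the plan applies them, none of the tests in the left column contrasts the arms. Kruskal-Wallis is in addition a test for independent samples, whereas the three conditions are repeated measures on the same patients.

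**2. Reproducing the plan's sample size**

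Inputs from the power paragraph: p_T = 0.80, p_P = 0.30, ratio k = 4, alpha 0.05, power 0.90. Pooled proportion = (0.30 + 4 × 0.80)/5 = 0.70.

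n_P = [z_alpha × sqrt(0.70 × 0.30 × (1 + 1/4)) + 1.2816 × sqrt(0.30 × 0.70 + 0.80 × 0.20/4)]² / 0.50²

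- One-sided (1.645): [1.645 × 0.5123 + 1.2816 × 0.5]² / 0.25 = 8.80, so 9 placebo and 36 DFN-15. This matches the plan.
- Two-sided (1.960): 10.82, so 11 + 44.

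At 36 + 9 the same approximation gives 90.6% power one-sided and 83.9% two-sided. The printed size is therefore correct for its inputs, and only for a one-sided test.

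**3. Power at the planned 40 and 10 completers**

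The pooled statistic is Z = (p1 - p2)/sqrt(p(1 - p)(1/40 + 1/10)), evaluated over all 41 × 11 = 451 possible tables with exact binomial probabilities at 80% and 30%.

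- One-sided 5%: 92.7%.
- Two-sided 5%: 86.6%.
- Significant in favour of DFN-15: 133 tables one-sided, 117 two-sided. The difference of 16 tables carries 6.0% probability.

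One-sided size is 5.0% at a common rate of 30% and 5.3-5.7% at 50-80%. Two-sided size is 4.8% at 30% and 4.3-5.5% at 50-80%.

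**4. A result that sidedness decides**

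28/40 vs 4/10 (70% vs 40%): pooled p = 32/50 = 0.64; SE = sqrt(0.64 × 0.36 × 0.125) = 0.1697; Z = 0.30/0.1697 = 1.77. One-sided p = 0.039; two-sided p = 0.077.

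Listing chi-square beside Z does not settle the matter. The uncorrected chi-square is Z² (here 3.13), so it is the two-sided pooled Z test, with cut-off 3.84, i.e. |Z| = 1.96 against 1.645. A one-sided Z and a chi-square test can disagree, and the plan does not say which decides.

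**5. Direction**

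The outcome is a responder proportion, so 80% vs 30% means higher under treatment, while the text expects lower. Read literally as DFN-15 minus placebo with rejection at Z ≤ -1.645, power at 80% vs 30% is 3.5 × 10⁻⁶. The minus sign is harmless if the difference is placebo minus DFN-15, but the plan does not say so.

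**6. If both primaries were kept**

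Two independent tests at 5% each, with either one enough for success, give a family-wise error of 1 - 0.95² = 9.75%. Splitting alpha to 2.5% each leaves responder power at 40 vs 10 of 86.6% one-sided or 81.7% two-sided (exact). The within-patient endpoints cannot be powered from the documents, which give no SD or expected change.

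**The case against.** The strongest reply is that the documents largely resolve this themselves. The later text names one primary outcome, gives it a between-arm test, calls it the primary hypothesis and sizes the trial on it alone. The same Z test appears with alpha 5%, one tail and a critical value of -1.645, so a one-sided test is the natural reading. The word for lower looks like a slip beside 80% and 30%. The study describes itself as proof of concept. The sentence about comparing patients with themselves goes on to cite the wide normative range of thresholds, so it most naturally rejects normal reference values rather than the placebo arm.

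Much of this stands. The responder comparison probably governs, and if it does, the placebo response is controlled. The sentence about control subjects should carry no weight; the point rests on the listed tests, none of which compares arms. Two-sided power of 86.6% is not a broken promise, because 90% was claimed one-tailed. The 28/40 vs 4/10 example comes from a region with only 6.0% probability under the design assumptions.

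The contradiction remains. That the later text governs is the reader's inference, not a rule in the plan, and the only paragraph headed Primary endpoint says something else. The outcome-measures text does not repeat the one-sided choice and adds a test that is two-sided.

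**Conclusion.** The concern holds, and the text should be corrected before unblinding. The plan contradicts itself on how many primary endpoints it has, whether skin sensitivity is one of them, and whether success is judged within patients or against placebo. Followed as written, the Primary endpoint paragraph lets a before-after change count as success.

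On the responder comparison, open sidedness moves exact power between 92.7% and 86.6% and changes the verdict in 16 of 451 tables. These figures rest on the plan's 80% and 30%, its 40 and 10 completers, and a pooled Z test without continuity correction. The sample-size arithmetic itself is sound for a one-sided test.

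**What to change.** - **Primary.** Delete the statement of two primary endpoints and write instead: *The single primary endpoint is the proportion of patients whose headache intensity falls by more than 50% between the pre-dose score and the score 2 hours after dosing. DFN-15 is compared with placebo by a one-sided pooled Z test at 5%, using DFN-15 minus placebo; a higher proportion favours DFN-15.* The 2-hour point is the 120-minute re-examination in the During-migraine visit paragraph.
- **Direction.** In the power paragraph, change the expectation from lower to higher under treatment, and give the critical value the sign that matches the stated subtraction.
- **Within-patient analyses.** Label the pain-score and threshold analyses secondary or mechanistic. They suit Objective 2 but are not evidence of effect against placebo. Use the Friedman test already listed in place of Kruskal-Wallis.
- **Allodynia.** Keep the between-arm proportions as secondary.
- **If a two-sided test is preferred.** Say so and restate power as about 87% at 40 vs 10. Reaching 90% takes about 54-55 completers instead of 50 (exact power 90.5% at 43 + 11 and 89.8% at 44 + 11), which would change the stopping rule.
- **If two primaries are kept.** Give each a between-arm test, and state either an alpha split or that both must succeed.

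The recommended version costs wording only, since every value is already collected. Within-arm results lose confirmatory status. The sponsor should note that the one-sided pooled Z test slightly exceeds 5% at higher common rates, up to 5.7% at 80%.

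### Pain-threshold values are tested only within patients; the one DFN-15 versus placebo comparison of skin sensitivity uses dichotomised allodynia status, and the plan disagrees with itself on whether this endpoint is primary

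*Combined protocol and SAP*

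**What the plan says.** All of this is in the Data analysis section of the combined protocol and SAP.

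**Status of the endpoint.** The paragraph headed Primary endpoint announces two primary endpoints; "the second is reduction in skin sensitivity at 2 hours after DFN-15 treatment". Later the section gives a single one: "The primary outcome measure in the current study is the proportion of patients demonstrating a headache intensity decrease that is greater than 50"%. It continues: "Secondary outcome measures are proportions of patients demonstrating allodynia before and after treatment".

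**Tests of the threshold values.** The before-to-after differences are those "between before and after DFN-15 treatment will be computed on a pair-wise basis". For the three sessions, "Differences between pain-free vs. during untreated migraine vs. during treated migraine will be computed on a multiple sample pair-wise basis". Mean thresholds are judged "by using appropriate pair-wise multiple sample comparison (Newman-Keuls, Kruskal-Wallis) tests". A substitute is offered: "Alternatively, repeated measurements of pain thresholds (allodynia) will be analyzed using Friedman two-way analysis of variance". The stated reason for comparing patients with themselves is that the normative range is wide.

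**Tests by arm.** Z and chi-square tests "assess the categorical association between the group (treatment / placebo") and three binary outcomes: headache reduction above or below 50%, heat threshold above or below 41 °C, and pressure threshold above or below 30 g.

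The Study design section has thresholds measured in both arms two hours after dosing.

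**The concern.** The study is a randomised, placebo-controlled proof of concept on the mechanism of DFN-15 in allodynia, and Objective 2 asks whether allodynia can be reversed by late treatment. The threshold values are the most informative data for that question. As planned, they are only compared across sessions in the same patients.

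The plan does not say whether those session tests run in the DFN-15 arm, in each arm, or in both arms pooled. On none of these readings can they separate a drug effect from natural recovery between 3 and 5 hours after onset, or from placebo response. A significant before-to-after change could therefore be reported as a drug effect when there is none. If skin sensitivity is a primary endpoint, that would affect a main conclusion of the trial.

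**Working it through.** **1. Which analyses use the placebo arm as a comparator?**

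| Quantity | Planned test | DFN-15 vs placebo? |
|---|---|---|
| Threshold values, before vs after | pairwise differences | no |
| Threshold values, three sessions | Newman-Keuls, Kruskal-Wallis, or Friedman | no |
| Allodynia status (41 °C, 30 g) | Z / chi-square | yes |
| Headache reduction above 50% | Z / chi-square | yes |

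**2. The plan's own figure.** The only sample-size calculation is for headache: 80% vs 30%, one-sided 5%, power 90%, ratio 4:1. The pooled proportion is (0.3 + 4 × 0.8)/5 = 0.7.

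n(placebo) = [1.645 × √(0.7 × 0.3 × 1.25) + 1.282 × √(0.3 × 0.7 + 0.8 × 0.2/4)]² / 0.5² = (0.843 + 0.641)² / 0.25 = 8.8, so 9 placebo and 36 DFN-15, as stated. Nothing comparable is given for thresholds, so the steps below rest on assumptions.

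**3. Assumptions.** 40 and 10 completers (the stopping rule under Randomized controlled trial). The rest are not in the documents: normal thresholds with SD 1, a 1 SD fall in migraine, and between-session correlation ρ of 0.5 or 0.7.

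**4. Within-arm test when DFN-15 does nothing.** Both arms recover by the same d. For untreated vs treated in 40 patients, the noncentrality is d√40/√(2(1 − ρ)). With 78 error degrees of freedom the critical value is 1.99, so the chance of significant improvement is roughly Φ(noncentrality − 1.99).

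| d (SD) | ρ = 0.5 | ρ = 0.7 | Simulated Newman-Keuls |
|---|---|---|---|
| 0 | Φ(−1.99) = 2.3% | 2.3% | about 2.5% |
| 0.1 | Φ(0.63 − 1.99) = 9% | Φ(0.82 − 1.99) = 12% | 9–12% |
| 0.2 | Φ(1.26 − 1.99) = 23% | Φ(1.63 − 1.99) = 36% | 24–35% |
| 0.3 | Φ(1.90 − 1.99) = 46% | Φ(2.45 − 1.99) = 68% | 47–68% |
| 0.5 | Φ(3.16 − 1.99) = 88% | Φ(4.08 − 1.99) = 98% | 88–98% |

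Pooling the arms raises the last two rows to 55–78% and to 94% or more. Friedman across the three sessions rejects in about 100% of trials even at d = 0, because migraine itself lowers thresholds. A between-arm ANCOVA rejects in 5%.

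**5. Between-arm ANCOVA when there is a real difference.** The residual SD is √(1 − ρ²) = 0.866 or 0.714. The standard error is that times √(1/40 + 1/10) = 0.354, giving 0.306 or 0.252. The 95% CI half-width is 2.012 × SE = 0.62 or 0.51 SD. Power is roughly Φ(difference/SE − critical value):

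- 0.8 SD, two-sided: Φ(2.61 − 2.01) = 73% to Φ(3.17 − 2.01) = 88%; simulated 71–87%. One-sided, simulated 81–93%.
- 1.0 SD: simulated 89–97% two-sided and 94–99% one-sided.
- 0.5 SD: simulated 35–49% two-sided.

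**6. The planned Z test on 2-hour allodynia status, same model.** Let p be the proportion allodynic before treatment and z its normal quantile, with placebo recovery of 0.2 SD. The 2-hour proportions are Φ(z − 0.2) on placebo and Φ(z − 0.2 − δ) on DFN-15. Power is summed exactly over the two binomials (10 and 40), with pooled variance.

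| p | Placebo | DFN-15, δ = 0.8 | Power, two-/one-sided | DFN-15, δ = 1.0 | Power, two-/one-sided |
|---|---|---|---|---|---|
| 60% | 52% | 23% | 45 / 58% | 17% | 62 / 73% |
| 70% | 63% | 32% | 45 / 57% | 25% | 62 / 74% |
| 80% | 74% | 44% | 43 / 55% | 36% | 62 / 73% |
| 90% | 86% | 61% | 30 / 47% | 53% | 50 / 66% |

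Both sidednesses are shown because the plan's power analysis is one-tailed.

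**The case against.** **The plan already compares allodynia by arm.** It does, and this is the strongest reply. A reader might infer that skin sensitivity has no placebo control at all; the documents do not support that. The Z and chi-square tests use thresholds, respect randomisation, and give a reasonable answer to a question worded as reversal. Against them stand the loss of information from the cut-offs and the absence of any arm test for a reduction in skin sensitivity measured on the threshold scale.

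**Self-comparison is deliberate.** The reason given is the wide normative range. A reader might take the reference there to control subjects as a decision to set the placebo arm aside, but in that context it most likely means healthy controls. It is a reason not to use norms, and ANCOVA on the pre-treatment value keeps the self-comparison.

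**The error rates depend on an undocumented recovery.** This stands. It would be wrong to say that a false positive is likely whatever happens: at zero recovery the rate is about 2.5%, and at 0.1 SD it is 9–12%. It becomes substantial from about 0.3 SD. The plan's own 30% placebo headache response makes some recovery plausible but does not fix its size on thresholds.

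**Kruskal-Wallis on repeated sessions.** It assumes independent groups, so it is the wrong label. Here it errs on the conservative side (size at most 0.4%) and is a minor matter.

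**Conclusion.** The point holds in a limited form. The two statements of the endpoint's status conflict and must be reconciled. Apart from the valid but dichotomised comparison of allodynia status, no planned test of the threshold values compares DFN-15 with placebo, so a before-to-after change in them cannot be credited to DFN-15. This follows from the text and needs no assumed figure.

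The size does rest on assumptions. With no drug effect, the false-attribution rate runs from about 2.5% to 98% as common recovery goes from 0 to 0.5 SD. In efficiency, ANCOVA has clearly more power than the planned Z test at 0.8 and 1.0 SD on either sidedness: at 0.8 SD, 71–87% against 30–45% two-sided, and 81–93% against 47–58% one-sided.

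The headache responder comparison is between arms and is not touched by this. The change should be made, but the trial does not fail without it.

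**What to change.** State whether skin sensitivity is primary or secondary. If primary, add a multiplicity rule across heat, von Frey and headache; even two independent tests at 5% would give 1 − 0.95² = 9.75%. Then add to the SAP:

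> The 2-hour heat threshold will be compared between DFN-15 and placebo by ANCOVA adjusted for the pre-treatment threshold. The 2-hour von Frey number, being ordinal, will be compared by rank ANCOVA adjusted for the pre-treatment value; this choice is fixed in advance. Arm differences will be reported with 95% CIs. The allodynia proportions by arm are kept. Within-patient session comparisons, including the untreated-to-treated change shown separately by arm, will use paired methods rather than Kruskal-Wallis. They are descriptive and will not be used to infer a drug effect.

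Friedman alone would not serve for the session comparisons: it is an omnibus test and cannot isolate untreated versus treated.

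The cost is wording only, since every variable is already measured. The limits remain. With 10 placebo patients the 95% CI half-width is about 0.51–0.62 SD, and power is low for differences below about 0.8 SD. Any bias from analysing only patients who complete all three sessions is not removed.
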